SAS	Statistical Analysis System®

Protocol Number: ARQ-151-313

Sponsor: Arcutis Biotherapeutics, Inc.

SCORAD	Scoring Atopic Dermatitis
SD	Standard Deviation
SE	Standard Error
SOC	System Organ Class
TEAE	Treatment Emergent Adverse Event
TESAE	Treatment Emergent Serious Adverse Event
TLF	Tables, Listings, and Figures
WHO-DD	World Health Organization Drug Dictionary
WI-NRS	Worst Itch - Numeric Rating Score
vIGA-AD	validated Investigator Global Assessment scale for Atopic Dermatitis

 Innovaderm Research	STATISTICAL ANALYSIS PLAN, Final Version 1.0
Protocol Number: ARQ-151-313	Sponsor: Arcutis Biotherapeutics, Inc.

1 INTRODUCTION

This Statistical Analysis Plan (SAP) describes the planned analysis and reporting for Arcutis Biotherapeutics, Inc. clinical protocol ARQ-151-313. The analyses described in the SAP are based upon the protocol Amendment 1 dated 17 September 2021. In case of changes (note that any such changes are described in section 3.6 below) between the protocol and the SAP, the SAP will be used to guide the statistical analysis. Deviations from the SAP are not expected. If any, they will be described and justified in the final Clinical Study Report (CSR), as appropriate.

This version of SAP has been developed and finalized prior to ARQ-151-313 database lock for the first Interim Analysis (IA).

Each IA will be performed only after the following steps have been completed: approval of this SAP, clinical trial data up to a pre-specified data cut-off date are entered into the database for subjects from parent studies ARQ-151-311 and ARQ-151-312 and any discrepancies in the data are resolved, finalization of the classification as important or non-important of each protocol deviation that occurred before or on the pre-specified data cut-off date for subjects from parent studies ARQ-151-311 and ARQ-151-312, and the database is locked. That is, subjects from parent study ARQ-151-315 will not be included in the IAs.

Similarly, the final analysis will be performed only after the following steps have been completed: approval of this SAP, clinical trial data are entered into the database for all subjects and any discrepancies in the data are resolved, finalization of the classification as important or non-important of each protocol deviation, and the database is locked.

ARQ-151 Cream 0.15% and ARQ-151 Cream 0.05% will be described as “roflumilast cream 0.15%” and “roflumilast cream 0.05%” throughout this document and the tables, listings, and figures (TLFs).

2 STUDY OBJECTIVES AND ENDPOINTS

OBJECTIVES	ENDPOINTS
Safety	
To assess long-term safety in subjects with atopic dermatitis (AD) treated with Roflumilast cream 0.15%	Primary safety endpoints: 
 • Treatment-emergent Adverse Events (TEAEs) • Serious Adverse Events (SAEs)

Protocol Number: ARQ-151-313

Sponsor: Arcutis Biotherapeutics, Inc.

OBJECTIVES	ENDPOINTS

once daily (QD; subjects \geq6 years of age) or Roflumilast cream 0.05% QD (subjects 2 to 5 years of age) after completing one of three Phase 3 studies (ARQ-151-311 or ARQ-151-312 or ARQ-151-315).
	
Other safety endpoints:
 
 Changes and percent change in clinical laboratory results Changes and percent change in vital signs Local tolerability assessments Change from baseline of Patient Health Questionnaire depression scale (PHQ-8) and Modified PHQ-9 for Adolescents (PHQ-A) total score Change from baseline of Children's Depression Inventory 2nd Edition (CDI-2) total score Columbia-Suicide Severity Rating Scale (C-SSRS)

Efficacy
 
To evaluate the long-term efficacy in subjects with AD treated with roflumilast cream 0.15% QD (subjects \geq6 years of age) or roflumilast cream 0.05% QD (subjects 2 to 5 years of age) after completing one of three Phase 3 studies (ARQ-151-311 or ARQ-151-312 or ARQ-151-315).
	
Secondary efficacy endpoints:
 
 Validated Investigator Global Assessment-Atopic Dermatitis (vIGA-AD) score of clear (0) or almost clear (1) at each assessment vIGA-AD success (defined as vIGA-AD score of clear (0) or almost clear (1) plus at least a 2-grade improvement from baseline) at each assessment In subjects \geq 12 years old at the start of the parent study, change and percent change from baseline in Worst Itch - Numeric Rating Score (WI-NRS) over time ^a Change and percent change from baseline in Eczema Area and Severity Index (EASI) total score over time 
Other efficacy endpoints:
 
 Duration of the first twice weekly (BIW) dosing interval Cumulative time (days) on BIW dosing

Protocol Number: ARQ-151-313

Sponsor: Arcutis Biotherapeutics, Inc.

OBJECTIVES	ENDPOINTS
	
 • Percent of time on BIW dosing • Duration (days) of the first disease control interval • Cumulative time (days) with disease control • Percent of time with disease control • Duration (days) of the first vIGA-AD score of Clear (0) • Cumulative time with vIGA-AD score of Clear (0) • Percent of time with vIGA-AD score of Clear (0) • Duration (days) of the first vIGA-AD score of Clear (0) or Almost Clear (1) • Cumulative time with vIGA-AD score of Clear (0) or Almost Clear (1) • Percent of time with vIGA-AD score of Clear (0) or Almost Clear (1) • Change and percent change from baseline in vIGA-AD score over time • In subjects \geq 12 years old at the start of the parent study with baseline WI-NRS \geq 4, achievement of at least a 4-point reduction on the WI-NRS over time ^a • Achievement of at least a 50%, 75%, 90%, 100% reduction in the EASI total score (EASI-50, EASI-75, EASI-90, EASI-100) over time • Change and percent change from baseline Body Surface Area (BSA) affected by AD over time • Change and percent change from baseline in Dermatology Life Quality Index (DLQI), Children's Dermatology Life Quality Index (CDLQI), Infants' Dermatitis Quality of Life (IDQOL) over time • Change and percent change from baseline in the Dermatitis Family Impact (DFI) over time • Change and percent change from baseline in the Scoring Atopic Dermatitis (SCORAD) over time

	STATISTICAL ANALYSIS PLAN, Final Version 1.0
Protocol Number: ARQ-151-313	Sponsor: Arcutis Biotherapeutics, Inc.

OBJECTIVES	ENDPOINTS
	
 Change and percent change from baseline in the Patient-oriented Eczema Measure (POEM) over time.
Pharmacokinetic	
To assess the systemic exposure of roflumilast and its N-oxide metabolite	
 Plasma concentrations of roflumilast and its N-oxide metabolite

^a Subjects < 12 years old will be included in subgroup analyses (refer to Section 6.6).

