5.5 Derived Variables

All questionnaire scores will be derived by Biostatistics in the ADaM datasets using the formulas defined below, even if calculated scores are present in the EDC database. All pre-calculated scores will be ignored for analysis.

- With the following exception, vIGA-AD Score of Clear (0) or Almost Clear (1) = vIGA-AD of ‘Clear’ (0) or ‘Almost Clear’ (1). The exception is that for subjects who discontinued early from study due to an AE or lack of efficacy, the subject will be considered as not having a vIGA-AD score of Clear (0) or Almost Clear (1) for all pre-specified analysis visits (refer to Section 5.4) for which the subject’s day of last dose falls within or is before the start of the analysis visit window.
- With the following exception, vIGA-AD Success = vIGA-AD of ‘Clear’ (0) or ‘Almost Clear’ (1) plus at least a 2-grade improvement from baseline. The exception is that for subjects who discontinued early from study due to an AE or lack of efficacy, the subject will be considered as not having a vIGA-AD success for all pre-specified analysis visits (refer to Section 5.4) for which the subject’s day of last dose falls within or is before the start of the analysis visit window. vIGA-AD Success will be derived for both the Primary and OLE baselines (refer to Section 5.2)
- Date of last contact = the latest of last study visit date, last dose date, end-of-study date and end-of-treatment date.
- Post-OLE Week 4 study duration (days): The duration can be represented as End Date – Start Date +1. The start date of the Post-OLE Week 4 interval will be the date of the OLE Week 4 visit or OLE Day 29 if the subject missed the OLE Week 4 visit. The end date will be the date of last contact. This endpoint will be calculated only for subjects who enter the post-OLE Week 4 study period.
- Duration (days) of the first BIW dosing will be calculated from the first BIW dosing to the start of the succeeding QD dosing interval. Subject’s last contact date will be used to censor

 Innovaderm Research	STATISTICAL ANALYSIS PLAN, Final Version 1.0
Protocol Number: ARQ-151-313	Sponsor: Arcutis Biotherapeutics, Inc.

this endpoint (time-to-event analysis) or as the end date of this duration (analyzed as a continuous endpoint) for subjects who do not revert to a QD dosing regimen after the first BIW dosing. This endpoint will be calculated only for subjects who enter the post-OLE Week 4 study period with at least one BIW dosing interval.

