- Cumulative time (days) on BIW dosing: Subjects may have more than 1 BIW dosing interval. The duration of succeeding BIW dosing intervals will be derived in a manner similar to the first and durations will be summed across all intervals for a subject. This endpoint will be calculated only for subjects who enter the post-OLE Week 4 study period with at least one BIW dosing interval.
- Percent of time on BIW dosing: The cumulative time (days) on BIW dosing will be divided by the Post-OLE Week 4 study duration and multiplied by 100 to measure the percentage of study days on BIW dosing. This endpoint will be calculated only for subjects who enter the post-OLE Week 4 study period with at least one BIW dosing interval.
- Duration (days) of first disease control will be calculated from the first disease control to the time subjects revert to a QD dosing or have a vIGA-AD score ≥ 2 , whichever comes first. Disease control is defined as achievement of a vIGA-AD score of 0, a switch to BIW dosing, and maintenance of a vIGA-AD score of 0 or 1. Disease control starts with the later date of a vIGA-AD score of Clear (0) on or after OLE Week 4 and the switch to BIW dosing. Subject's last contact date will be used to censor this endpoint (time-to-event analysis) or as the end date of this duration (analyzed as a continuous endpoint) for subjects who never lose disease control after the start of the first disease control interval. This endpoint will be calculated only for subjects who enter the post-OLE Week 4 study period and had at least one disease control interval.
- Cumulative time (days) with disease control. Subjects can come in and out of disease control. The duration for each interval will be derived as described above for the first interval. Cumulative time with disease control will sum the durations for all intervals where disease was under control as defined in the previous bullet. This endpoint will be calculated only for subjects who enter the post-OLE Week 4 study period and had at least one disease control interval.
- Percent of time with disease control. The cumulative time with disease control will be divided by the Post-OLE Week 4 study duration and multiplied by 100 to express cumulative time as a percentage of the duration of time that each subject spent in the study after OLE Week 4. This endpoint will be calculated only for subjects who enter the post-OLE Week 4 study period and had at least one disease control interval.

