 Innovaderm Research ■■■	STATISTICAL ANALYSIS PLAN, Final Version 1.0
Protocol Number: ARQ-151-313	Sponsor: Arcutis Biotherapeutics, Inc.

- Duration (days) of the first vIGA-AD of Clear (0) will be calculated from the first vIGA-AD score of 0 during the study to the next vIGA-AD score > 0. Subject's last contact date will be used to censor this endpoint (time-to-event analysis) or as the end date of this duration (analyzed as a continuous endpoint) for subjects who never revert to a vIGA-AD score > 0. This endpoint will be calculated only for subjects who had at least one vIGA-AD score of Clear (0) interval.
- Cumulative time (days) with vIGA-AD of Clear (0). Subjects can have more than 1 vIGA-AD of Clear (0) interval. The duration for each interval will be derived as described above for the first interval. Cumulative time with vIGA-AD of 0 will sum the durations for all intervals. This endpoint will be calculated only for subjects who had at least one vIGA-AD score of Clear (0) interval.
- Percent of time with vIGA-AD of Clear (0). The cumulative time will be divided by the study duration and multiplied by 100 to express cumulative time as a percentage of the duration of time that each subject spent in the study. This endpoint will be calculated only for subjects who had at least one vIGA-AD score of Clear (0) interval.
- Duration (days) of the first vIGA-AD of Clear (0) or Almost Clear (1) will be calculated from the first vIGA-AD score of 0 or 1 during the study to the next vIGA-AD score > 1. Subject's last contact date will be used to censor this endpoint (time-to-event analysis) or as the end date of this duration (analyzed as a continuous endpoint) for subjects who never revert to a vIGA-AD score > 1. This endpoint will be calculated only for subjects who had at least one VIGA-AD with a score of Clear (0) or Almost Clear (1) interval.
- Cumulative time (days) with vIGA-AD of Clear (0) or Almost Clear (1). Duration with vIGA-AD score of 0 or 1 measures the duration for the first interval with a VIGA-AD score of 0 or 1. There can be more than 1 interval. Cumulative time with vIGA-AD of 0 or 1 will sum the durations for all intervals. The duration for each interval will be derived as described above for the first interval. This endpoint will be calculated only for subjects who had at least one VIGA-AD with a score of Clear (0) or Almost Clear (1) interval.

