12.3.1 Main Analysis

Missing other efficacy endpoints will not be imputed.

Duration, cumulative time, and percent of time endpoints will be summarized using descriptive statistics by treatment group (refer to Section 5) and two-sided 95% CI of the mean will also be provided.

For duration endpoints, the number and percentage of subjects experiencing a status change or censored will be provided overall and by treatment group, along with reason for censoring. Additionally, these endpoints will also be analyzed using Kaplan–Meier (KM) method. The KM estimates of the time-to-event will be provided overall and by treatment group for the 25th, 50th (median), and 75th percentiles along with their corresponding two-sided 95% CI. The estimates of the SEs will be computed using the Greenwood's formula. The two-sided 95% CI for the survival function at the 25th, 50th, and 75th percentiles will be calculated according to Brookmeyer and Crowley (1982)². KM curves will be provided overall and by treatment group.

Dichotomic, change from baseline, and percent change from baseline endpoints will be summarized similarly as the secondary efficacy endpoints (refer to Section 12.2).

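### The Kaplan-Meier first-interval durations censor subjects who leave for lack of efficacy or an AE with no event recorded, and no sensitivity analysis shows what that does to the percentiles

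*SAP*

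**What the plan says.** SAP 2 lists four first-interval durations among the other efficacy endpoints, one of them "Duration (days) of the first disease control interval". SAP 5.5 gives each its own event and censors the rest at last contact:

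- **BIW dosing:** ends at the start of the next QD interval. It is censored "for subjects who do not revert to a QD dosing regimen after the first BIW dosing".
- **Disease control:** runs "from the first disease control to the time subjects revert to a QD dosing", or to a vIGA-AD of 2 or more if that is earlier. The subject's "last contact date will be used to censor this endpoint (time-to-event analysis") "for subjects who never lose disease control after the start of the first disease control interval".
- **vIGA-AD 0:** ends at the next score above 0, with a parallel censoring rule.
- **vIGA-AD 0/1:** ends at the next score above 1. It is censored "for subjects who never revert to a vIGA-AD score > 1".

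None of the four definitions refers to the reason for leaving. For the two vIGA-AD responder endpoints the same section does: "for subjects who discontinued early from study due to an AE or lack of efficacy, the subject will be considered as not having" the response, from the analysis window that holds the last dose onward. SAP 6.2.1 also removes such subjects' later vIGA-AD data before imputation, citing the parent studies' primary estimand.

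SAP 12.3.1 states: "The KM estimates of the time-to-event will be provided overall and by treatment group", at the 25th, 50th and 75th percentiles. It adds curves and counts of events and censored subjects, with the reason for censoring. SAP 12.3.2 rules out sensitivity analyses for this tier of endpoints.

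**The concern.** Kaplan-Meier assumes that a censored subject has the same outlook as those still followed. That is hard to defend for a subject who leaves because the treatment is not working. Protocol 4.6.1 allows no rescue treatment, so leaving is one of the outcomes open to a subject whose disease is not controlled.

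The same person can then be a non-responder in the secondary vIGA-AD endpoints and a censored observation in the maintenance curve. These curves carry weight: SAP 6.6 builds subgroup analyses on the BIW and disease control durations in order to study long-term maintenance. If losses of response leave the event count through censoring, the reported percentiles are lengthened, and no planned analysis shows by how much.

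**Working it through.** **1. Who is exposed.** Consider a subject with an open first interval who leaves for lack of efficacy without having restarted QD.

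| Duration | Early termination vIGA-AD of 2 or more | No worse score recorded |
|---|---|---|
| BIW dosing | censored (only QD restart is an event) | censored |
| Disease control | event | censored |
| vIGA-AD 0 | event | censored |
| vIGA-AD 0/1 | event | censored |

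A QD restart before leaving is an event for the first two durations but not for the two score-based ones. Protocol 5.5 asks for the Week 52 assessments at early termination, including vIGA-AD, so a relapse present at exit can be captured for three of the four durations. It cannot be captured for BIW dosing.

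**2. Direction.** Suppose a censored observation becomes an event at the same or an earlier date. Last dose is never later than last contact, which SAP 5.5 defines as the latest of four dates that include last dose. Such a change can only lower the Kaplan-Meier curve or leave it as it is. The planned percentiles are therefore equal to or longer than those under the responder rule.

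**3. Size.** The plan states no expected median, event rate or dropout rate, so there is no figure to reproduce. The rest is illustration on assumed inputs.

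Let *L* be the hazard of recorded loss and *m* the hazard of lack-of-efficacy or AE exit without a recorded event, both constant. The median is ln 2 / *L* if exits are censored and ln 2 / (*L* + *m*) if they are events. Follow-up from Week 4 to Week 52 is 48 × 7 = 336 days.

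Example with a 200-day median and 10% exits over 336 days:

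- *L* = 0.6931 / 200 = 0.003466 per day
- *m* = −ln(0.90) / 336 = 0.000314 per day
- Median with exits as events = 0.6931 / 0.003779 = 183.4 days
- Ratio = 200 / 183.4 = 1.09

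| Assumed exits over 336 days | Median, censored | Median, exits as events | Excess |
|---|---|---|---|
| 1% | 200 | 198.3 | 0.9% |
| 3% | 200 | 194.9 | 2.6% |
| 5% | 200 | 191.6 | 4.4% |
| 10% | 200 | 183.4 | 9.0% |
| 15% | 200 | 175.5 | 14.0% |

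Across assumed medians of 120 to 280 days the excess is 0.5% to 1.2% at 1% exits and 8.4% to 19.5% at 15%.

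**4. Effect of losses already recorded.** A simulation (300 subjects, 336 days, 200 replicates, true median 200 days) varied the share of leavers who already had an event on record. Mean medians in days, censored versus event:

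| Exits | None recorded | Half recorded | 90% recorded |
|---|---|---|---|
| 3% | 201.2 vs 197.1 | 197.9 vs 196.3 | 197.8 vs 197.7 |
| 5% | 201.6 vs 194.4 | 197.4 vs 194.3 | 194.6 vs 194.4 |
| 10% | 201.1 vs 184.5 | 191.8 vs 184.4 | 185.8 vs 184.8 |

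The gap depends almost wholly on how many exits have no event recorded.

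**The case against.** A reader might infer that everyone who leaves for lack of efficacy or an AE is censored as still maintained. The documents do not support that.

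- Only subjects without a recorded event are censored. Worsening on maintenance leads to a phone call and QD dosing, and a vIGA-AD of 2 or more at a clinic visit does the same (SAP 3.1). Both routes generate events before exit.
- Subjects who never responded are outside these analyses, because each duration is calculated only for subjects who had such an interval.

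The difference from the responder rule is also not a contradiction. That rule is written for the two vIGA-AD responder endpoints. SAP 5.5 has no counterpart for the EASI or WI-NRS responder definitions, and no estimand is stated for the durations. For a subject still clear who leaves for an unrelated AE, no loss of control has occurred and censoring is defensible.

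The constant-hazard arithmetic is a simplification too. vIGA-AD is scheduled at Weeks 4, 12, 24, 36 and 52, so the score-based durations will move largely in visit-sized steps, and a percentile may not move at all. The stakes are limited: these rank below the secondary endpoints, and no hypothesis tests are planned (SAP 5.7).

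All of this stands, and it limits the point. It does not remove it. For BIW dosing the early termination visit gives no protection. For disease control, a subject at vIGA-AD 1 with inadequately controlled symptoms who leaves for lack of efficacy is censored. Tabulating the reason for censoring shows how many such subjects there are, but not what they do to the curve.

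**Conclusion.** The point holds in limited form. Among subjects with an open first interval, those who leave for lack of efficacy or an AE with no qualifying event recorded are censored at last contact. For lack-of-efficacy exits that censoring is informative, most clearly for BIW duration. The Kaplan-Meier percentiles are equal to or longer than under the rule that the SAP applies to its vIGA-AD responder endpoints.

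The size cannot be derived from the documents. On the assumptions above it ranges from under 1 day (3% exits, 90% already recorded) to about 17 days on a 200-day median (10% exits, none recorded). These figures rest on constant hazards and invented exit rates.

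Two stronger conclusions are tempting and go too far. One is that the durations are overstated by a material amount: no discontinuation rate in either document supports that. The other is that such exits must be events in the main analysis. That is a choice of estimand, and it would turn BIW duration into time to QD or discontinuation. The point concerns the Kaplan-Meier analysis only; the parallel continuous summary takes last contact as the end of the interval.

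**What to change.** 1. In SAP 12.3.2, replace the statement that there will be no sensitivity analyses with a Kaplan-Meier sensitivity analysis of the four first-interval durations. It counts study discontinuation for lack of efficacy or an AE during an open interval as an event on the day of last dose. Show it also for lack of efficacy alone, since the case for censoring is stronger for AE exits.
2. In SAP 5.5, state which strategy the main analysis of these durations targets, so that the difference from the responder endpoints is a declared choice.
3. For programming, say how to treat an interval that opens only after the last dose (for example, a first clear score at the early termination visit), such as leaving it censored as now.

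The cost is one additional set of Kaplan-Meier outputs, in which the durations may be slightly shorter. Reasons for discontinuation are already collected for the disposition table (SAP 7.1), so no new data are needed.
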